2. ETHICAL CONSIDERATIONS

2.1 Good Clinical Practice

This study will be conducted in accordance with Good Clinical Practice (GCP), as defined by the International Conference on Harmonisation (ICH) and in accordance with the ethical principles underlying European Union Directive 2001/20/EC and the United States Code of Federal Regulations, Title 21, Part 50 (21CFR50).

The study will be conducted in compliance with the protocol. The protocol and any amendments and the subject informed consent will receive Institutional Review Board/Independent Ethics Committee (IRB/IEC) approval/favorable opinion prior to initiation of the study.

All potential serious breaches must be reported to BMS immediately. A serious breach is a breach of the conditions and principles of GCP in connection with the study or the protocol, which is likely to affect, to a significant degree, the safety or physical or mental integrity of the subjects of the study or the scientific value of the study.

Personnel involved in conducting this study will be qualified by education, training, and experience to perform their respective tasks.

This study will not use the services of study personnel where sanctions have been invoked or where there has been scientific misconduct or fraud (eg, loss of medical licensure, debarment).

2.2 Institutional Review Board/Independent Ethics Committee

Before study initiation, the investigator must have written and dated approval/favorable opinion from the IRB/IEC for the protocol, consent form, subject recruitment materials (eg, advertisements), and any other written information to be provided to subjects. The investigator or BMS should also provide the IRB/IEC with a copy of the Investigator Brochure or product labeling information to be provided to subjects and any updates.

The investigator or BMS should provide the IRB/IEC with reports, updates and other information (eg, expedited safety reports, amendments, and administrative letters) according to regulatory requirements or institution procedures.

2.3 Informed Consent

Investigators must ensure that subjects are clearly and fully informed about the purpose, potential risks, and other critical issues regarding clinical studies in which they volunteer to participate.

In situations where consent cannot be given to subjects, their legally acceptable representatives (as per country guidelines) are clearly and fully informed about the purpose, potential risks, and other critical issues regarding clinical studies in which the subject volunteers to participate.

BMS will provide the investigator with an appropriate (ie, Global or Local) sample informed consent form which will include all elements required by ICH, GCP and applicable regulatory

requirements. The sample informed consent form will adhere to the ethical principles that have their origin in the Declaration of Helsinki.

Investigators must:

- 1) Provide a copy of the consent form and written information about the study in the language in which the subject is most proficient prior to clinical study participation. The language must be non-technical and easily understood.
- 2) Allow time necessary for subject or subject's legally acceptable representative to inquire about the details of the study.
- 3) Obtain an informed consent signed and personally dated by the subject or the subject's legally acceptable representative and by the person who conducted the informed consent discussion.
- 4) Obtain the IRB/IEC's written approval/favorable opinion of the written informed consent form and any other information to be provided to the subjects, prior to the beginning of the study, and after any revisions are completed for new information.
- 5) If informed consent is initially given by a subject's legally acceptable representative or legal guardian, and the subject subsequently becomes capable of making and communicating his or her informed consent during the study, consent must additionally be obtained from the subject.
- 6) Revise the informed consent whenever important new information becomes available that is relevant to the subject's consent. The investigator, or a person designated by the investigator, should fully inform the subject or the subject's legally acceptable representative or legal guardian, of all pertinent aspects of the study and of any new information relevant to the subject's willingness to continue participation in the study. This communication should be documented.

The confidentiality of records that could identify subjects must be protected, respecting the privacy and confidentiality rules applicable to regulatory requirements, the subjects' signed ICF and, in the US, the subjects' signed HIPAA Authorization.

The consent form must also include a statement that BMS and regulatory authorities have direct access to subject records.

Subjects unable to give their written consent (eg, stroke or subjects with or severe dementia) may only be enrolled in the study with the consent of a legally acceptable representative. The subject must also be informed about the nature of the study to the extent compatible with his or her understanding, and should this subject become capable, he or she should personally sign and date the consent form as soon as possible. The explicit wish of a subject who is unable to give his or her written consent, but who is capable of forming an opinion and assessing information to refuse participation in, or to be withdrawn from, the clinical study at any time should be considered by the investigator.

The rights, safety, and well-being of the study subjects are the most important considerations and should prevail over interests of science and society.

3. INVESTIGATIONAL PLAN

3.1 Study Design and Duration

This is a Phase 2, multi-center, open-label, multiple cohort study of elotuzumab in combination with pomalidomide and low-dose dexamethasone (EPd Cohort) and elotuzumab in combination with nivolumab (EN Cohort) to assess the safety and efficacy of these combination therapies for treatment of relapsed or refractory MM patients.

In the EPd Cohort, subjects will receive treatment with elotuzumab in combination with pomalidomide and low-dose dexamethasone in a 28 day cycle. Subjects will receive 10 mg/kg IV elotuzumab on Days 1, 8, 15, and 22 of Cycles 1 and 2. Starting with Cycle 3, subjects will receive 20 mg/kg on Day 1.

As of Amendment 02, subjects will also be enrolled in the EN cohort to receive a combination of elotuzumab and nivolumab in a 28-day cycle. EN subjects will receive nivolumab 240 mg IV on Days 1 and 15 for Cycles 1-4. At Cycle 5 and beyond, subjects will receive 480 mg IV on Day 1. Subjects will also receive elotuzumab 10 mg/kg on Days 1, 8, 15, and 22 of Cycles 1 and 2. At Cycle 3 and beyond, subjects will receive 20 mg/kg of elotuzumab IV on Day 1. If subjects do not achieve clinical benefit represented by at least minimal response (\geq MR) after 2 cycles of treatment or do not achieve an objective response (\geq PR) after 5 cycles of treatment, they may cross over to the EPd cohort at Day 1 of the subsequent cycles if they also meet the eligibility criteria for cross-over specified in Section 3.3.4.

Subjects will continue treatment as long as the subject has clinical benefit from the treatment and do not meet criteria for discontinuation.

All subjects will be assessed for safety and response as presented in the Time and Event Tables in Section 5. Subjects who are discontinued from further study treatment for reasons other than progression will be followed for disease progression. Following disease progression, subjects will be followed at least annually for survival.

Approximately 120 subjects will be screened in this study. A minimum of 60 subjects will be treated in the EPd Cohort. Approximately 30 subjects will be treated in the EN Cohort. The estimated duration of enrollment is 18 to 24 months, and the duration of the study is estimated at 48 months from the date of first patient, first visit. Per Revised Protocol 03, the EPd cohort is closed for enrollment.

The study design schematic is presented in Figure 3.1-1.

3.2 Post Study Access to Therapy

At the conclusion of the study, subjects who continue to demonstrate clinical benefit are eligible to receive BMS supplied study drug. Study drug will be provided via an extension of the study, a rollover study requiring approval by responsible health authority and ethics committee or through another mechanism at the discretion of BMS. BMS reserves the right to terminate access to BMS supplied study drug if any of the following occur: a) the marketing application is rejected by responsible health authority; b) the study is terminated due to safety concerns; c) the subject can obtain medication from a government sponsored or private health program; or d) therapeutic alternatives become available in the local market.

3.3 Study Population

For entry into the study, the following criteria MUST be met.

3.3.1 Inclusion Criteria

1. Signed Written Informed Consent

- a) Subject is, in the investigator's opinion, willing and able to comply with the protocol requirements.
- b) Subject has given voluntary written informed consent before performance of any study-related procedure not part of normal medical care, with the understanding that consent may be withdrawn by the subject at any time without prejudice to their future medical care.

2. Target Population

a) All subjects must have documented disease progression per IMWG (Appendix 4) criteria during or after their last anti-myeloma therapy.

Revised Protocol No.: 03 Date: 08-Mar-2018

- b) As of Amendment 02, this criterion has been moved to criterion 2.i.i for clarity.
- c) As of Amendment 02, this criterion has been moved to criterion 2.i.ii for clarity.
- d) Per Amendment 1, this criterion is no longer applicable. Specifications previously listed in criterion d) have been included in the revised criterion c) above.
- e) Measurable disease at screening, based on central laboratory results, defined as one or more of the following:
 - i) Serum IgG, IgA, IgM M-protein $\ge 0.5 \text{ g/dL}$
 - ii) Urinary M-Protein \ge 200 mg urinary M-protein excretion in a 24 hour collection sample
 - iii) Involved serum free light chain (sFLC) \geq 10 mg/dL provided the FLC ratio is abnormal.
- f) ECOG Performance Status ≤ 2 (Appendix 2).
- g) Subject Re-enrollment: This study permits the re-enrollment of a subject that has discontinued the study as a pre-treatment failure (ie, has not been treated). If re-enrolled, the subject must be re-consented.
- h) As of Amendment 02, this criterion has been moved to criterion 2.i.iii for clarity.
- i) for the EPd Cohort:
 - i) Subjects must have received at least 1 but no greater than 2 prior lines of therapy (note: induction and stem cell transplants with or without maintenance therapy is considered 1 line of therapy)
 - Subjects must have received prior treatment with a lenalidomide-containing regimen for at least 2 consecutive cycles (full therapeutic dose) and must have been deemed as relapsed, refractory, or intolerant. Refractory is defined as progressing on-treatment or within 60 days of the last dose.³⁰

NOTE: lenalidomide-based regimens to which the subject has relapsed or been refractory to is not required to be the most recent regimen received.

- iii) Prior elotuzumab exposure is permitted only if subjects fulfill all of the following:
 - (1).Did not discontinue elotuzumab due to any intolerable drug-related adverse reaction.
 - (2).Did not participate in a prior elotuzumab clinical trial, regardless of treatment assignment
- j) For EN Cohort:
 - i) Subjects must have received at least 4 prior lines of therapy including a proteasome inhibitor (PI), an immunomodulatory (IMID) agent, and an anti-CD38 antibody.

3. Age and Reproductive Status

- a) Males and Females, at least 18 years or legal age of consent per local regulations
- b) Women of childbearing potential (WOCBP) must have a negative serum or urine pregnancy tests (minimum sensitivity 25 IU/L or equivalent units of HCG), at 10-14 days prior to start of study drug; another within 24 hours prior to the start of study drug.
- c) Women must not be breastfeeding
- d) WOCBP must agree to follow instructions for method(s) of contraception for 1 month (4 weeks) before the start of treatment with study drugs, for the duration of treatment with study drugs, and for a total of 5 months post-treatment completion.

- e) Males who are sexually active with WOCBP must always use a latex or synthetic condom during any sexual contact with females of reproductive potential while taking pomalidomide and for up to 28 days after discontinuing pomalidomide, even if they have undergone a successful vasectomy. Male patients must not donate sperm.
- f) Azoospermic males and WOCBP who are continuously not heterosexually active are exempt from contraceptive requirements. However, they must still undergo pregnancy testing as described in this section.
- g) All subjects must be willing and able to comply with the local pomalidomide risk management program or the Pomalidomide Pregnancy Risk Prevention Plan
- h) All subjects must agree not to share study medication.
- i) Male subjects receiving elotuzumab or nivolumab must also agree to follow instructions for method(s) of contraception for 1 month (4 weeks) before the start of treatment with study drugs, for the duration of treatment with study drugs, and for a total of 7 months post-treatment completion.
- j) Subjects must be willing to refrain from blood donations during study drug therapy and for 90 days after therapy.

Investigators shall counsel WOCBP and male subjects who are sexually active with WOCBP on the importance of pregnancy prevention and the implications of an unexpected pregnancy Investigators shall advise WOCBP and male subjects who are sexually active with WOCBP on the use of highly effective methods of contraception. Highly effective methods of contraception have a failure rate of < 1% when used consistently and correctly.

At a minimum, subjects must agree to the use of two methods of contraception, with one method being highly effective and the other method being either highly effective or less effective as listed below:

HIGHLY EFFECTIVE METHODS OF CONTRACEPTION

- Male condoms with spermicide
- Hormonal methods of contraception including combined oral contraceptive pills, vaginal ring, injectables, implants and intrauterine devices (IUDs) such as Mirena® by WOCBP subject or male subject's WOCBP partner. Female partners of male subjects participating in the study may use hormone based contraceptives as one of the acceptable methods of contraception since they will not be receiving study drug
- IUDs, such as ParaGard®
- Tubal ligation
- Vasectomy
- Complete Abstinence*

*Complete abstinence is defined as complete avoidance of heterosexual intercourse and is an acceptable form of contraception for all study drugs. Female subjects must continue to have pregnancy tests. Acceptable alternate methods of highly effective contraception must be discussed in the event that the subject chooses to forego complete abstinence.

LESS EFFECTIVE METHODS OF CONTRACEPTION

- Diaphragm with spermicide
- Cervical cap with spermicide
- Vaginal sponge
- Male Condom without spermicide
- Progestin only pills by WOCBP subject or male subject's WOCBP partner
- Female Condom*
- * A male and female condom must not be used together

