The effect of pomalidomide on spermatogenesis is not known and has not been studied. Therefore, male patients taking pomalidomide must meet the following conditions (ie, all males must be counselled concerning the following risks and requirements prior to the start of pomalidomide study therapy):

- Understand the potential teratogenic risk if engaged in sexual activity with a pregnant female or a female of childbearing potential
- Understand the need for the use of a condom even if he has had a vasectomy, if engaged in sexual activity with a pregnant female or a female of childbearing potential.

Contraception

Females of childbearing potential (FCBP) enrolled in this protocol must agree to use two reliable forms of contraception simultaneously or to practice complete abstinence from heterosexual contact during the following time periods related to this study: 1) for at least 28 days before starting study drug; 2) while participating in the study; 3) dose interruptions; and 4) for at least 28 days after study treatment discontinuation.

The two methods of reliable contraception must include one highly effective method and one additional effective (barrier) method. FCBP must be referred to a qualified provider of contraceptive methods if needed. The following are examples of highly effective and additional effective methods of contraception:

- Highly effective methods:
 - → Intrauterine device (IUD)
 - → Hormonal (birth control pills, injections, implants)
 - \rightarrow Tubal ligation
 - → Partner's vasectomy
- Additional effective methods:
 - \rightarrow Male condom
 - → Diaphragm
 - \rightarrow Cervical Cap

Because of the increased risk of venous thromboembolism in patients with multiple myeloma taking pomalidomide and dexamethasone, combined oral contraceptive pills are not recommended. If a patient is currently using combined oral contraception the patient should

switch to another one of the effective methods listed above. The risk of venous thromboembolism continues for 4–6 weeks after discontinuing combined oral contraception. The efficacy of contraceptive steroids may be reduced during co-treatment with dexamethasone.

Implants and levonorgestrel-releasing intrauterine systems are associated with an increased risk of infection at the time of insertion and irregular vaginal bleeding. Prophylactic antibiotics should be considered particularly in patients with neutropenia.

Pregnancy testing

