Medically supervised pregnancy tests with a minimum sensitivity of 25 mIU/mL must be performed for females of childbearing potential, including females of childbearing potential who commit to complete abstinence, as outlined below.

Before starting study drug

Female Patients:

FCBP must have two negative pregnancy tests (sensitivity of at least 25 mIU/mL) prior to starting study drug. The first pregnancy test must be performed within 10-14 days prior to the start of study drug and the second pregnancy test must be performed within 24 hours prior to the start of study drug. The patient may not receive study drug until the study doctor has verified that the results of these pregnancy tests are negative.

Male Patients:

Must practice complete abstinence or agree to use a condom during sexual contact with a pregnant female or a female of childbearing potential while participating in the study, during dose interruptions and for at least 28 days following study drug discontinuation, even if he has undergone a successful vasectomy.

During study participation and for 28 days following study drug discontinuation

Female Patients:

- → FCBP with regular or no menstrual cycles must agree to have pregnancy tests weekly for the first 28 days of study participation and then every 28 days while on study, at study discontinuation, and at day 28 following study drug discontinuation. If menstrual cycles are irregular, the pregnancy testing must occur weekly for the first 28 days and then every 14 days while on study, at study discontinuation, and at days 14 and 28 following study drug discontinuation.
- → At each visit, the Investigator must confirm with the FCBP that she is continuing to use two reliable methods of birth control.
- → Counselling about pregnancy precautions and the potential risks of fetal exposure must be conducted at a minimum of every 28 days.
- → If pregnancy or a positive pregnancy test does occur in a study patient, study drug must be immediately discontinued.

- → Pregnancy testing and counselling must be performed if a patient misses her period or if her pregnancy test or her menstrual bleeding is abnormal. Study drug treatment must be discontinued during this evaluation.
- → Females must agree to abstain from breastfeeding during study participation and for at least 28 days after study drug discontinuation.

Male Patients:

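### Section 3.3.1 both requires condom use (item 3.e) and waives it (item 3.f) for a man on pomalidomide who is azoospermic after vasectomy and sexually active with women of childbearing potential

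*Protocol*

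**What the plan says.** The rules for men are in protocol Section 3.3.1, under Age and Reproductive Status.

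- **Item 3.e** covers men who are sexually active with WOCBP. They "must always use a latex or synthetic condom during any sexual contact with females of reproductive potential while taking pomalidomide", and the duty continues "for up to 28 days after discontinuing pomalidomide, even if they have undergone a successful vasectomy".
- **Item 3.f** reads: "Azoospermic males and WOCBP who are continuously not heterosexually active are exempt from contraceptive requirements". The next sentence adds: "However, they must still undergo pregnancy testing as described in this section".
- **Item 3.g** requires all subjects to be willing and able to comply with either the local pomalidomide risk management program or the Pomalidomide Pregnancy Risk Prevention Plan (Appendix 6).
- **Item 3.i** adds a separate duty: "Male subjects receiving elotuzumab or nivolumab must also agree to follow instructions for method(s) of contraception", lasting until 7 months after treatment completion.

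Appendix 6 repeats the condom rule. Its counselling text (1.1.1.1) expects a male patient to "Understand the need for the use of a condom even if he has had a vasectomy" if he has sexual contact with a pregnant female or a female of childbearing potential. Its rules for male patients continue the duty "for at least 28 days following study drug discontinuation, even if he has undergone a successful vasectomy". The counselling form (1.1.1.2) also includes vasectomised men and gives the period simply as 28 days. The opening lines of Appendix 6, which misnumber it as Appendix 5, limit it to subjects on clinical supply of pomalidomide and send those on commercial supply to the REMS program.

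**The concern.** Items 3.e and 3.f are consecutive entries in one list, and each is written without exception. One says that a successful vasectomy does not end the condom duty. The other ends contraceptive duties for men who are azoospermic, which is what a successful vasectomy would ordinarily be taken to mean. Two sites could give the same kind of man opposite instructions, and each could point to a numbered criterion in support.

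What is at stake is partner and fetal safety. Section 4.3.3 describes pomalidomide as an analogue of thalidomide, a known human teratogen, and Appendix 6 says that its effect on spermatogenesis has not been studied. Appendix 6 also applies the condom rule when the partner is already pregnant. In that text the rule therefore does more than prevent conception, whereas 3.f exempts a man on fertility status alone.

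**Working it through.** No arithmetic applies. The check sets the texts side by side.

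| Question | Item 3.e | Item 3.f | Appendix 6 |
|---|---|---|---|
| Which men? | Sexually active with WOCBP, taking pomalidomide | Azoospermic | Male patients on clinical supply of pomalidomide |
| Condom required? | Yes | Exempt from contraceptive requirements | Yes, or complete abstinence |
| Effect of vasectomy | Does not lift the rule | Not mentioned | Does not lift the rule |
| Exception for azoospermia | None | This is the exemption | None |
| Exception for pomalidomide | Not applicable | None | Not applicable |
| Post-treatment period | 28 days as a maximum | None | 28 days as a minimum; plain 28 days on the form |

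1. **Overlap.** Take a man who had a successful vasectomy, is azoospermic as a result, takes pomalidomide and is sexually active with WOCBP. Item 3.e binds him by its own vasectomy clause, and 3.f releases him by the word azoospermic.
2. **Is the condom a contraceptive requirement?** The method lists that follow in Section 3.3.1 include the male condom, with spermicide among the highly effective methods and without it among the less effective ones. Nothing takes the condom in 3.e outside the scope of 3.f.
3. **Does the phrase about not being heterosexually active also qualify the men?** Grammatically it could. Then 3.f would reach only azoospermic men who are not sexually active, and the conflict would vanish because 3.e covers only men who are. But the word azoospermic would then do no work. The sentence that follows, on pregnancy testing, cannot apply to men at all, which suggests that the item was not checked for them. At best the text is ambiguous.
4. **Precedence.** Neither 3.e nor 3.f refers to the other. Item 3.g imposes a program on everyone but does not say that it overrides 3.f.
5. **Period after treatment.** Read literally, a man who stops using condoms before day 28 can satisfy 3.e but not Appendix 6. This difference exists only for subjects on clinical supply.
6. **Who is reached.** Men on EPd, and EN men who cross over. EPd is closed to enrollment, so new pomalidomide starts come only through cross-over. Section 3.3.4 sets response conditions for cross-over, states no reproductive criteria of its own and does not require re-consent.

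**The case against.** The strongest answer is that the specific rule governs the general one. Item 3.e names vasectomised men and uses emphatic wording, and the method list counts vasectomy as only one of at least two methods required, so the drafters evidently thought of these men as bound. Item 3.f does not stand alone either. Item 3.g makes every subject follow a pomalidomide program. Section 1.5 requires full compliance with the distribution program, and Section 4.3.3 allows dispensing only to those who meet all its conditions. Where Appendix 6 applies, counselling that covers vasectomised men is documented before each dispensing. Finally, the protocol neither defines azoospermia nor equates it with vasectomy.

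Much of this stands as a limit on the consequences. A reader might infer that sites will release these men from the condom rule. The documents do not show that, given these safeguards; nor do they rule it out for commercial supply, because the REMS terms are not in them. None of the safeguards removes the conflict in the text, since no order of precedence is stated.

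Three stronger readings are tempting and are not supported:

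- **That the plan gives four different requirements, including the 7 months in 3.i.** Item 3.i is worded as an additional duty and is tied to elotuzumab or nivolumab. A man can meet 3.e and 3.i together, and 3.f can be read as an exception to 3.i without contradiction. The 7 months are not part of the conflict.
- **That Appendix 6 binds every man on pomalidomide.** It covers clinical supply only, and the text under Table 4.-1 says that pomalidomide is obtained through the site's standard prescribing procedures. The documents do not say how many subjects, if any, are on clinical supply.
- **That every azoospermic or vasectomised man is affected.** Item 3.e reaches only those sexually active with WOCBP while on pomalidomide.

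The mention of pregnant partners in Appendix 6 but not in 3.e is a matter of clarity rather than a contradiction, because the WOCBP definition in Section 3.3.3 does not exclude pregnant women.

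**Conclusion.** The point holds in a narrow form. Items 3.e and 3.f contradict each other for men who are azoospermic after vasectomy, take pomalidomide and are sexually active with WOCBP. The contradiction lies within Section 3.3.1 and does not depend on Appendix 6. For subjects on clinical supply there is a second inconsistency, between a 28-day maximum in 3.e and a 28-day minimum in Appendix 6.

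The conclusion rests on two readings: that a successful vasectomy makes a man azoospermic, and that the qualifier about sexual activity in 3.f belongs to WOCBP only. Both are the ordinary readings, but the protocol states neither. The number of men concerned cannot be derived from the documents. Endpoints, sample size and analyses are untouched. The inconsistency should be corrected because it concerns partner safety and costs little to remove.

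**What to change.** Reconcile items 3.e and 3.f of Section 3.3.1 with each other and with Appendix 6, so that one consistent instruction applies to azoospermic and vasectomised men on pomalidomide. In the same edit, settle the 28-day wording across 3.e, the Appendix 6 rules for male patients and the counselling form, and state how item 3.g relates to 3.f. Which rule applies, and for how long, is for the sponsor to decide. Item 3.i need not change for this purpose.

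The cost is a wording change in Section 3.3.1 and Appendix 6 at the next amendment, with no added visits or procedures.

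### Section 3.3.1 accepts combined oral contraceptive pills for the female subject herself, while Appendix 6 advises against them in women taking pomalidomide and dexamethasone

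*Protocol*

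**What the plan says.** Section 3.3.1 of the protocol requires two contraceptive methods, at least one of them highly effective. Its list of highly effective methods contains "Hormonal methods of contraception including combined oral contraceptive pills, vaginal ring, injectables, implants and intrauterine devices (IUDs", and the entry goes on to name the users: "such as Mirena® by WOCBP subject or male subject's WOCBP partner". The list makes no distinction by cohort or regimen. The same entry explains that partners of male subjects may use hormonal methods because they take no study drug. That reason does not cover the female subject.

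Appendix 6 (Section 1.1.1.1, under Contraception) takes a different position on the pill: "Because of the increased risk of venous thromboembolism in patients with multiple myeloma taking pomalidomide and dexamethasone, combined oral contraceptive pills are not recommended". A current user should "switch to another one of the effective methods listed above". It adds: "The risk of venous thromboembolism continues for 4–6 weeks after discontinuing combined oral contraception". It also warns that dexamethasone may make contraceptive steroids less effective.

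Two further provisions bear on this. Section 1.5 and inclusion criterion 3(g) require subjects to comply with a pomalidomide distribution or risk programme. The opening of Appendix 6 limits that appendix to clinical supply of pomalidomide and sends commercial supply to the REMS programme. Section 4 says that pomalidomide is obtained through the site's usual prescribing.

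**The concern.** The two texts give a site different guidance about the same woman. Screened against Section 3.3.1, a combined pill counts as a highly effective method. Read against Appendix 6, she should be moved off it.

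What is at stake is subject safety, not inference. The protocol already treats thrombosis as a live risk: exclusion 2(d) in Section 3.3.2 removes subjects who cannot tolerate thromboembolic prophylaxis. Accepting the combined pill adds a risk that could be avoided. The dexamethasone warning matters too, because Section 4.3.3 describes pomalidomide as an analogue of a known human teratogen.

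The route for new exposure is crossover. EN women first receive pomalidomide when they move to EPd. Section 3.3.4 gives response conditions for that move, does not mention contraception, and says re-consent is not needed.

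**Working it through.** There is no planned figure to reproduce. The check compares the texts and then does a short timing calculation.

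**Does any other text correct the Section 3.3.1 list?**

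1. *The programme duty (Section 1.5, criterion 3(g)).* It binds subjects to a programme but does not amend the list of methods or mention the combined pill.
2. *Scope of Appendix 6.* The warning formally applies to clinical supply. For commercial supply, Section 4.3.3 and the opening of Appendix 6 point to REMS, whose contraceptive rules are not in the documents.
3. *Checks within Appendix 6.* The investigator confirms two reliable methods at each visit, and the counselling document bars dispensing if two were not used. These checks count methods. The counselling document itself lists birth control pills among the highly effective methods and carries no thromboembolism warning. A woman using a combined pill and a condom would pass them.
4. *Section 4.5.1.* It requires contraception before pomalidomide starts but does not say which kind.

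So nothing in the available text removes or qualifies the combined pill in Section 3.3.1.

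**Timing for an EN woman who crosses over.** Inputs: residual risk 4–6 weeks (Appendix 6); 28-day cycles with starts anchored to Cycle 1 Day 1 (Section 4.5.8); crossover on Day 1 of the next cycle, after 2 or after 5 cycles (Section 3.1 and the Synopsis).

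- Residual risk in days: 4 × 7 = 28 to 6 × 7 = 42. In cycles: 28/28 = 1.0 to 42/28 = 1.5.
- Earliest crossover: 2 × 28 = 56 days after Cycle 1 Day 1. Later crossover: 5 × 28 = 140 days.
- Pill stopped on the crossover day: 28–42 days of residual risk run into pomalidomide treatment.
- Pill stopped at Cycle 2 Day 1, which is 28 days before the earliest crossover: 28 − 28 = 0 to 42 − 28 = 14 days remain.
- Pill stopped at Cycle 1 Day 1: the period ends 56 − 42 = 14 to 56 − 28 = 28 days before the earliest crossover, and 140 − 42 = 98 to 140 − 28 = 112 days before the later one.

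A switch made only when crossover happens is therefore late by the protocol's own statement of the risk. A switch when EN treatment starts is in time for either crossover point.

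**The case against.** The strongest reply is that the texts can be read together. Section 3.3.1 sets a minimum and sorts methods by efficacy. The programme duty adds to that minimum, and Appendix 6 itself lists birth control pills as highly effective before giving its safety advice. On this reading Section 3.3.1 lacks a cross-reference but contradicts nothing. Much of this stands: the programme duty is binding, and Section 3.3.1 does not encourage the pill. It does not close the gap, because a reader of Section 3.3.1 sees the combined pill accepted for the subject without qualification, and the appendix that qualifies it does not formally cover every supply route.

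It is also fair to say that stopping the pill on the crossover day is the worst case. Appendix 6 calls for counselling before pomalidomide, and for contraception from at least 28 days before it. It sets no washout for the pill.

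Four stronger readings are tempting and are not supported:

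- *That the protocol permits something it forbids.* Appendix 6 advises against the combined pill; it does not prohibit it.
- *That Section 3.3.1 wrongly lets two barrier methods suffice.* It classes "Male condoms with spermicide" as highly effective and asks for two methods, "with one method being highly effective and the other method being either highly effective or less effective as listed below". Appendix 6 says: "The two methods of reliable contraception must include one highly effective method and one additional effective (barrier) method". But the Appendix 6 lists are given as examples and do not mention spermicide, so the clash has to be inferred.
- *That all hormonal methods should go because of dexamethasone.* The statement is only that efficacy may be reduced, Appendix 6 keeps hormonal methods on its list, and a second method is required in any case.
- *That women receive no thromboembolism warning.* Section 3.4, which includes the thromboprophylaxis text cited as 3.4.1, and the Information Sheet that each patient must read are not in the available text. Either might contain one.

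**Conclusion.** The inconsistency is real and minor. For a woman on pomalidomide plus dexamethasone, Section 3.3.1 accepts one named method, the combined oral contraceptive pill, that Appendix 6 advises against on thromboembolic grounds. The available text does not resolve it.

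Its reach is small. EPd is closed to enrolment, so new exposure comes through EN crossover, and EN is about 30 subjects. The documents do not give the number of women of childbearing potential, of crossovers, or of EPd women still on treatment, so no expected number affected can be stated. Nothing in the endpoints, sample size or analyses changes.

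The conclusion assumes that the unseen Section 3.4 and Information Sheet do not already qualify the list. How far the Appendix 6 warning formally applies also depends on the supply route and on REMS rules that are not in the documents. The thromboembolic reason concerns the drugs, so the clinical point does not depend on who supplies them.

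**What to change.** In Section 3.3.1, for female subjects receiving pomalidomide plus dexamethasone, including EN women before crossover:

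- remove combined oral contraceptive pills from the accepted methods, and keep them for partners of male subjects;
- state that current users should switch to another listed method;
- state the 4–6 week residual risk, so that EN women considering crossover can switch in time;
- confirm before the first pomalidomide dose that the method in use is not a combined pill.

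A compulsory change for every EN woman at entry is not needed, since many may never receive pomalidomide. Telling them early about the residual period is enough.

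Two clarifications are optional: a sentence saying that the stricter of Section 3.3.1 and the applicable pomalidomide programme applies, and a correction to the opening line of Appendix 6, which calls itself Appendix 5.

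The cost is a few sentences. No visit or test is added, because the method check fits the contact before the first pomalidomide dose. The one downside is that some EN women who never cross over may change their pill.
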